5.5.5 Clinical samples

At each visit, participants will have clinical samples collected according to the sampling schedule outlined in table 1.

5.5.5.1 Oropharyngeal swab

Oropharyngeal swabs will be collected from each participant using standard techniques. After sample collection, the swab be aseptically placed in liquid Amies (or similar) transport solution and maintained at 2-8°C in a cold box until processing in the laboratory. Study nurses collecting the sample will take care to use appropriate personal protective equipment (PPE). Detailed procedures for swab collection and transport will be outlined in the relevant study specific procedure.

Oropharyngeal swabs will be collected in exactly the same way for participants complaining of symptoms that could be consistent with acute pharyngitis at unscheduled visits

5.5.5.2 Normal skin swab

Normal skin swabs will be collected with the intention of identifying any GAS present on the skin, rather than differentiating skin site. It is not clear which skin sites are most likely to be colonized by GAS, therefore in order to maximise sensitivity, multiple skin sites will be swabbed with the same swab.

Swabs will be obtained using modification of a standard skin microbiota swabbing technique (24-27) in which the swab head is soaked in sterile saline solution prior to skin swabbing. The swab will be taken from 2cm by 2cm squares of skin on the forehead, both forearms both lower legs, and then placed aseptically in liquid transport medium and stored at 2-8°C in a cold box until processing in the laboratory.

5.5.5.3 Pyoderma wound swab

Pyoderma skin swabs will be taken in the field from any participants with evidence of pyoderma. Pus will be expressed if necessary. Skin swabs will be placed in liquid transport medium until they reach the lab. They will be refrigerated at approximately 2-8°C in cool boxes until arrival at the laboratory.

5.5.5.4 Dried blood spot

Dried blood spot (DBS) samples will be collected onto dried blood spot collection cards from a finger prick on the participant. The finger will be cleansed with alcohol and allowed to dry before the finger prick is made. The DBS collection card will be left to dry at room temperature overnight before processing. Storage and transportation will be at room temperature.

5.5.5.5 Blood sampling

The study team will be trained to perform venepuncture on site. In the case that the head of the household, all participants aged over 18, and all guardians of children under 18 verbally consent to venepuncture for blood to be taken on site, this will be performed within the household. An alternative option will be given to every household, for an appointment to be made at a specified time to attend Sukuta Health Centre, where venepuncture for blood serum will be performed by members of the study team.

Blood will be taken from participants using peripheral venepuncture by a trained nurse or doctor from the study team. Blood samples will be collected in serum separation tubes using aseptic technique, ensuring appropriate PPE is used. Training will be provided based on the specifics outlined in the study specific protocol governing this process.

Blood serum samples will not be obtained from participants under the age of 2 years.

5.5.5.6 Salivary samples

Salivary samples will be collected using an oracol swab from participants at the time points specified in table 1. Training will be provided on sample collection for the study team based on the specifics outlined in the study specific protocol governing this process. Once obtained, the swab will be immediately placed in the collection tube according to the manufacturer's instructions.

5.5.5.7 Additional clinical samples

Any additional blood or other samples (e.g. urine) required for the routine clinical assessment and care of a participant may be obtained in the field or at MRCG clinical services as indicated with the verbal consent of the participant or parent/guardian of participants under 18 years.

5.5.5.8 Environmental swabbing

At monthly household visits, environmental swabs will be taken from common touch points in the household. At the enrolment visit, an assessment will be made by the study team lead to identify 2 surfaces to swab within the household which are commonly touched by multiple people and are rarely cleaned. This decision will be made collaboratively with the study team taking advice from the household members. Such potential swabbing points might include door handles, table surfaces, curtains, benches, chair handles etc. Once 2 surfaces have been decided for the household, those will be the 2 surfaces swabbed at each subsequent visits.

Environmental swab collection technique will be described in detail in the relevant study specific protocol governing the process. One swab will be used for each swabbing point. The swab tip will be soaked in sterile saline solution prior to swabbing, and will be rubbed slowly and thoroughly over the surface (up to 50cm) 3 times reversing direction between strokes. Once collected, the swab will be aseptically placed in liquid transport medium, and stored at 2-8°C in a cold box until processing in the laboratory.

For the personal and household hygiene visit, additional environmental swabs will be collected from a wider range of common touch points in the house, and a swab will be soaked in water taken from the household greywater source.

5.5.5.9 Settle plates

A settle plate will be used at each monthly household visit to passively capture the presence of airbourne GAS within households. A culture petri dish pre-prepared with blood agar will be placed at a suitable point in the main social indoor room of the household e.g. the parlour, sitting room, or main shared bedroom. Ideal placement of the settle plate would be at least 1 metre off the floor, 1 metre away from the walls and other large obstacles. The plate will be left for 1 hour, then retrieved and stored at 2-8°C in a cold box until processing in the laboratory.

5.6 Laboratory evaluations

5.6.1 Sample transport

All swabs and clinical samples taken in the field, with the exception of DBS collection cards, will be stored as soon as possible in a cold box maintained at 2-8°C and transported to the MRCG Fajara laboratories for processing the same day.

5.6.2 Culture procedures

Oropharyngeal, pyoderma, normal skin and environmental swabs will be processed in the same way. Swabs will arrive at the laboratory in 1ml of liquid transport medium (STGG, Amies or similar). On arrival at the lab, after ensuring that the swab is inside and the lid is properly closed, the swab will be briefly vortexed in the transport medium. After vortexing, the swab will be removed and streaked onto a blood agar culture plate, and then discarded. The remaining transport medium will be stored at -70°C for subsequent use if reculturing is required, and for PCR analysis. Prior to storage the transport

medium may be separated into various aliquots. The detailed procedure will be outlined in the relevant study specific protocol.

The culture plates will be incubated overnight at 37°C and assessed for the presence of beta-haemolytic colonies. Colonies with clear beta-haemolysis will be picked and replated for purity overnight at 37°C. The following day, the colonies will be identified using catalase testing, and if negative then latex agglutination testing for Lancefield group A, C and G. Catalase positive colonies will be tested for *Staphylococcus aureus* using latex testing.

Any group A, C or G streptococci isolates identified will then be stored in glycerol broth at -70°C for later revival, DNA extraction and whole genome sequencing (WGS). *S. aureus* colonies will also be stored for later analysis.

Antimicrobial susceptibility testing by disc diffusion using standard CLSI procedures will also be performed on group A, C or G streptococcal isolates identified.

5.6.3 Quantitative PCR

Reserved transport medium from some samples will undergo quantitative PCR testing using GAS-specific (spy-gene or other GAS-specific target) real-time PCR. Stored aliquots will undergo DNA extraction followed by quantitative PCR in order to obtain a measure of GAS bacterial load. The detailed procedures for the PCR will be outlined in the relevant study specific protocol.

5.6.4 Whole genome sequencing (WGS)

Isolates will be revived, and DNA extracted using established methods at MRCG. Library preparations and WGS (illumina Miseq) will be undertaken at the MRCG genomics facility. Quality control (fastqc), *de novo* genome assembly (SPAdes) and core genome determination (roary) will be done, followed by basic phylogenetic reconstruction using maximum likelihood (RAxML). A state-of-the-art tool (phyloscanner (28)) will be utilised to determine genotypically-linked isolates by analysing genetic diversity and relationships within and between cases simultaneously.

5.6.5 Dried blood spot (DBS) sampling

Whole blood will be collected from finger or heel prick in the field. Six drops will be collected onto DBS collection cards. Collection cards will be dried at room temperature overnight, they can then be stored at room temperature or refrigerated. Upon processing in the laboratory, 6mm punches of dried blood filter paper will be obtained, which will be eluted using a buffer solution. The resulting eluate will then undergo serological analysis for anti-GAS antigens, including streptolysin O, SpyCEP, SpyAD, GAC, and M protein.

5.6.6 Serum blood

Serum blood samples will be used to assess serological activity to GAS antigens including streptolysin O, SpyCEP, SpyAD, GAC, and M protein at baseline and at the end of the cohort. Serum blood taken at the same time-points as DBS samples will additionally contribute to validation of DBS in this setting as a reliable and reproducible assay for anti-GAS proteins. Serum samples will be stored for further immunological work including streptococcal killing assays and opsonophagocytic assays in order to explore correlates of protection from GAS asymptomatic carriage and clinical disease.

5.6.7 Salivary samples

Salivary samples will be used to assess for mucosal antibody activity to GAS antigens including streptolysin O, SpyCEP, SpyAD, GAC, and M protein. Samples will be stored for further immunological work.

5.7 Modelling

By utilising the novel data in this project, it will allow estimation of relative contributions of between and within household transmission, and transmission between symptomatic and asymptomatic individuals. A mathematical model of GAS household transmission will be designed based on the data from this study. The model will be calibrated using a combination of clinical and behavioural data, and use phylogenetic relatedness of isolates to identify transmission events between study participants. The household model will also be valuable in evaluating potential intervention strategies for future implementation within LMICs.

6 Safety and treatment considerations

As this study is observational and does not involve an investigational product, adverse events will not be formally recorded and there is no data safety monitoring board. However, while participants are enrolled in the study, the study team is responsible for certain aspects of their medical care, in particular with respect to GAS infections.

6.1 Diagnosis and management of GAS infections

6.1.1 Definition of GAS-related disease

6.1.1.1 GAS pharyngitis

Acute pharyngitis (including tonsilitis) is usually defined as inflammation of the pharynx or tonsils with an acute onset. GAS is only one potential cause of acute pharyngitis, and viral infection is the most common cause. Of bacterial infections, GAS infection is the most common, but others include *Streptococcus pneumoniae*, *Haemophilus influenzae* and *Bordetella pertussis*. There are additionally a small number of fungal and non-infectious causes.

For the purpose of this study it is necessary to distinguish between:

1. **Asymptomatic colonisation** of the pharynx with GAS and **symptomatic infection** of the pharynx by GAS
and
2. **Symptomatic infection** of the pharynx by GAS and **symptomatic inflammation** of the pharynx by another infectious or non-infectious cause

Therefore, we will use the following definitions:

Asymptomatic pharyngeal GAS colonisation

GAS identified on culture from a swab taken from the oropharynx of a participant who at the time of sampling did not complain of any of the following symptoms: *fever, sore throat, difficulty swallowing, cough, or hoarse voice, and on clinical examination did not have any of the following features: inflammation or erythema of the pharynx, tonsils, palate or epiglottis, pus or exudate on the tonsils, swelling of the cervical or submandibular lymph nodes, a scarlatiniform rash, or petechiae on the palate.*

Acute GAS pharyngitis

GAS identified on culture from a swab taken from the oropharynx of a participant who at the time of sampling did complain of any of the following symptoms: *fever, sore throat, difficulty swallowing, cough, or hoarse voice, or on clinical examination did have any of the following features: inflammation or erythema of the pharynx, tonsils, palate or epiglottis, pus or exudate on the tonsils, swelling of the cervical or submandibular lymph nodes, a scarlatiniform rash, or petechiae on the palate.*

Acute pharyngitis from a non-GAS cause

GAS not identified on culture from a swab taken from the oropharynx of a participant who at the time of sampling did complain of any of the following symptoms: *fever, sore throat, difficulty swallowing, cough, or hoarse voice, or on clinical examination did have any of the following features: inflammation or erythema of the pharynx, tonsils, palate or epiglottis, pus or exudate on the tonsils, swelling of the cervical or submandibular lymph nodes, a scarlatiniform rash, or petechiae on the palate.*

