At each visit an oropharyngeal (OPS), normal skin swab (NSS), oral fluid (OF) and dried blood spot (DBS) will be taken from all individuals present, data collected on socio-demographics, behavioural factors and clinical examination findings. In addition, a blood sample for serum (BS) may be taken at the beginning and end of the study for detailed functional immune responses. This may be done by arranging a clinic visit if more appropriate. Swabs will also be taken from any pyoderma lesions, from common touch points in the household such as door handles, and settle plates (SP) used inside households. Throughout the study, if an enrolled participant reports symptoms consistent with GAS infection, they will have an unscheduled visit including a physical examination an appropriate swab (oropharyngeal or pyoderma), OF and DBS. Swabs will be taken the same day to the research microbiology laboratory and plated for culture. The culture will identify the presence of GAS (and Groups C and G Streptococcus) from the swabs, antibiotic resistance will be determined and any GAS (and GCS and GGS) isolates will be stored for later use. Skin and pyoderma swabs will also be cultured for *Staphylococcus aureus* and isolates stored for later use. Additional clinical samples will be taken at various time-points including serum blood samples, dried blood spot and salivary samples to contribute to exploratory objectives.

Swabs from participants will be cultured for the presence of GAS and isolates will undergo whole genome sequencing (WGS) in order to assess phylogenetic relatedness of strains identified. These data, combined with temporal incidence of strain acquisition, clinical data and household situation will be used to build a mathematical model of GAS transmission to identify key routes of transmission within and between households.

[figure not shown]

Figure 1. Visit and sampling schedule schematic

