5.3.2 Enrolment visit (MV0)

At the enrolment visit (MV0), each individual will undergo a baseline survey including participant's sociodemographic data, medical history and social-mixing/behavioural factors. A physical examination will be carried out including a full body examination (taking care to maintain privacy) looking for any evidence of skin infections, and swabs will be collected from the oropharynx and from normal skin. Additionally, a salivary sample will be obtained, and blood will be taken for a serum sample and dried blood spot. Any individual who is exhibiting symptoms of pharyngitis (sore throat and pharyngeal inflammation) will be further examined and managed as they would be at an unscheduled visit for possible GAS infection (see section 5.3.4 below). Any individual who is identified as having evidence of pyoderma (bacterial skin infection involving pus or crusts), will have a wound swab taken, and will be provided antibiotic treatment according to WHO or local guidelines as appropriate. Any additional abnormal finding requiring further investigation or treatment will be managed according to local practice or an appropriate referral made according to the nature of the finding (see section 5.3.4).

Alongside the individual surveys, data will be collected for each household such as household setup, family relationships, sleeping arrangements, presence of mosquito nets, number of rooms, number

of buildings and access to water points. Environmental swabs will be taken from common touch points such as door handles and soft furnishings, and settle plates will be used indoors to investigate airborne transmission.

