5.3.6 Weekly visits for asymptomatic GAS (or GCS/GGS) carriers

All participants not already in the intensified incident GAS cohort, who's OPS or NSS grow GAS (or GCS/GGS) on culture at a monthly visit following a previous negative swab, will be classified as "new carriers" who will then be swabbed weekly until such time as 2 negative swabs in a row have been obtained from the same site that was positive i.e. a participant who's OPS was positive at MV1 will have weekly OPS until negative twice in a row, whereas a participant with a positive NSS will have weekly NSS.

At these weekly visits, only the household member who is a "new carrier" will be seen and swabbed, not the other household members. The study team will ask a brief medical history, perform a physical examination, and take the swab from the previous positive site. If the participant has developed any clinician symptoms potentially in connection with their positive swab, then they will be treated as a GAS infection case as described in section 5.3.4.

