6.2.2 Non-study related diagnoses

All other non-study related diagnoses will be managed or referred on by the study nurses as appropriate according to best local practice. In particular however, unnecessary antibiotic treatment will be avoided, and where there is doubt, the on-call study physician will be consulted. Any fever will be investigated with a malaria RDT in the first instance, and any participant presenting with symptoms meeting the criteria for COVID-19 testing will be referred to the MRCG CSD for appropriate investigation, isolation and management.

7 Discontinuation criteria

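### A GAS-positive throat swab plus one non-specific feature counts as acute GAS pharyngitis, so carriers with an unrelated illness are classed as clinical cases

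*Protocol*

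**What the plan says.** Section 6.1.1.1 opens with a clinical description: "Acute pharyngitis (including tonsilitis) is usually defined as inflammation of the pharynx or tonsils with an acute onset". It adds that "GAS is only one potential cause of acute pharyngitis, and viral infection is the most common cause". It then names two separations that the study has to make: colonisation of the pharynx from GAS infection, and GAS infection from inflammation with another cause.

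Three definitions follow, all built on one list of symptoms and signs.

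- **Acute GAS pharyngitis:** positive culture, with fever or "sore throat, difficulty swallowing, cough, or hoarse voice, or on clinical examination did have any of the following features". Any one symptom or any one sign suffices. Cough, fever, hoarse voice or a swollen cervical or submandibular node each qualifies alone.
- **Asymptomatic pharyngeal colonisation:** positive culture with none of the listed features. Among GAS-positive participants this is the exact complement.
- **Non-GAS pharyngitis:** "GAS not identified on culture from a swab taken from the oropharynx of a participant who at the time of sampling did complain" of any feature on the same list, or showed any listed sign.

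On sampling, section 3.1 states: "At each visit an oropharyngeal (OPS), normal skin swab (NSS), oral fluid (OF) and dried blood spot (DBS) will be taken" from everyone present, whatever their symptoms. Section 2.1 makes the prevalence and incidence of clinical GAS infection primary endpoints. Primary objective 2 (section 2) covers risk factors for pharyngeal infection, including its relationship with carriage.

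**The concern.** The three definitions differ only in the culture result and in whether any listed feature is present. Among people with a feature, culture alone assigns the cause. Culture shows that GAS is in the throat. It does not show that GAS explains the cough or fever. The rule therefore cannot make the two separations that the section calls necessary.

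The protocol itself expects listed features from other causes. Section 6.2.2 says: "Any fever will be investigated with a malaria RDT in the first instance", and provides for COVID-19 referral. A throat carrier whose fever is explained by malaria still meets the definition of acute GAS pharyngitis. Judgement about cause appears elsewhere: section 5.3.6 refers to symptoms "potentially in connection with their positive swab", and section 6.1.2 allows the assessor to decide that GAS is unlikely. Neither judgement enters the definition.

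A study that swabbed only sore throats would seldom meet the problem. This one swabs everyone present at up to 13 scheduled visits and will find such carriers. The risk is an inflated pharyngitis count, some loss from asymptomatic carriage, and a distorted relation between carriage and disease in objective 2, where carriage is itself part of what makes a case.

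**Working it through.** The protocol states no pharyngitis rate, so there is no figure of its own to reproduce. Its sample size rests on carriage and is not affected.

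**Inputs**

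- *t*, true GAS pharyngitis per visit: 1% (assumed).
- *P*, throat carriage: 5% (assumed) and 15%. The latter is the section 8 planning figure for skin and throat pooled, so it is a ceiling for the throat alone.
- *s*, chance of at least one listed feature unrelated to GAS: 2% and 10% of visits (assumed).
- Coincidental features are taken as independent of carriage. Treatment is ignored.
- About 450 people (section 8) and 13 scheduled visits (MV0 to MV12), none missed: 450 × 13 = 5,850 visits.

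**Recorded pharyngitis and coincidental share**

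Recorded prevalence = t + P·s. Coincidental share = P·s / (t + P·s).

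| P | s | P·s | Recorded | Coincidental share | False labels, 5,850 × P·s |
|---|---|---|---|---|---|
| 5% | 2% | 0.1% | 1.1% | 0.1/1.1 = 9% | about 6 |
| 15% | 2% | 0.3% | 1.3% | 0.3/1.3 = 23% | about 18 |
| 5% | 10% | 0.5% | 1.5% | 0.5/1.5 = 33% | about 29 |
| 15% | 10% | 1.5% | 2.5% | 1.5/2.5 = 60% | about 88 |

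Low case: with P = 2% (the bottom of the range that section 8 quotes for children in high-income countries) and s = 2%, P·s = 0.04%. Then 5,850 × 0.0004 = 2.3, so about 2 false labels in the whole study.

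**Asymptomatic carriage**

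Recorded carriage is P(1 − s). From 5% it falls to 4.9% or 4.5%; from 15% it falls to 14.7% or 13.5%. The loss is modest.

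**Objective 2, direction only**

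- *Prior carriage.* If carriage persists between visits, a prior carrier is more likely than a non-carrier to be culture-positive now. The coincidental term P·s is then larger in prior carriers, and an association can appear even where true pharyngitis is unrelated to prior carriage.
- *A factor that doubles true pharyngitis but is unrelated to coincidental positives.* Its recorded ratio is (2t + P·s) / (t + P·s), which is below 2 whenever P·s > 0. The association is diluted.

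**Does a culture-negative comparison help?**

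Estimate true cases as (symptomatic positives − all positives × feature rate in negatives) / (1 − that rate), with all positives = t + P.

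- P = 15%, s = 10%: (2.5% − 16% × 0.10) / 0.90 = 0.9% / 0.90 = 1.0%.
- P = 5%, s = 2%: (1.1% − 6% × 0.02) / 0.98 = 0.98% / 0.98 = 1.0%.

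Both recover the assumed 1% in expectation, provided the independence assumption holds.

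**The case against.** A sensitive definition is a legitimate choice. Because the two GAS-positive classes are complements, the broad list keeps everyone with a symptom out of asymptomatic carriage, which is itself a primary endpoint and the basis of the sample size. Current symptoms and throat and node findings are recorded (sections 5.5.3 and 5.5.4), so a narrower class can be formed at analysis. At non-urgent unscheduled visits, section 5.3.4 calls for a swab only when symptoms fit possible GAS infection. Dried blood spots, antibody fold-change and qPCR on some samples could help to tell infection from carriage. All of this stands. It argues for keeping the broad class and against replacing it. It does not remove the problem at monthly visits, and none of the added information enters the definition.

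Three stronger readings are tempting, and the protocol does not support them.

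- *That pharyngitis prevalence and incidence are themselves primary endpoints.* Section 2.1 names clinical GAS infection, of which pharyngitis is one component beside pyoderma. The shares computed here apply to that component at monthly visits. Only objective 2 names pharyngeal infection directly.
- *That section 5.3.2 contradicts section 6.1.1.1.* It says: "Any individual who is exhibiting symptoms of pharyngitis (sore throat and pharyngeal inflammation) will be further examined". That determines who receives further examination and management at enrolment. It is not a rival endpoint definition.
- *That the inflation of the prior-carriage association can be quantified.* This would need carriage persistence, the effect of treatment and a rule for counting new episodes. The protocol supplies no values for the first two, and episode rules may properly sit in an analysis plan that is not shown.

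**Conclusion.** The point holds as a flaw in a rule that the protocol states explicitly. The definition cannot separate a throat carrier with an intercurrent illness from a case of GAS pharyngitis, and universal monthly swabbing means that such carriers will be met. The pharyngitis component of clinical GAS infection is biased upward, and the same people leave asymptomatic carriage. In objective 2 the association with prior carriage can be inflated, while associations with factors unrelated to coincidental positives can be diluted.

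The direction for prevalence follows from the definition. The size does not: it rests on assumed values for true pharyngitis, throat carriage and coincidental features. Within the ranges used, 9% to 60% of recorded pharyngitis at monthly visits is coincidental; at low carriage and feature rates the problem is negligible in absolute terms. This warrants an inexpensive change in classification and reporting. It is not a reason to redesign the study.

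**What to change.** For endpoint classification only, leaving care unchanged:

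1. Keep the section 6.1.1.1 definition as the broad class.
2. Within it, pre-specify a subclass of culture-positive participants with only non-specific features (fever, cough, hoarse voice or nodes alone). State where every listed feature belongs, including difficulty swallowing and scarlatiniform rash. Do not move this subclass into asymptomatic carriage.
3. Report the pharyngitis component of prevalence and incidence, and the pharyngeal part of objective 2, with the subclass included and excluded.
4. For objective 2, add a comparison of feature frequency in culture-positive and culture-negative participants.
5. State that carriers with a viral sore throat remain misclassified.

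The cost is a wording change and a few tabulations, using data already planned. The downsides are fewer events in the narrower analysis, some mild true cases counted only in the broad class, a third group that is neither clean carriage nor clear disease, and imprecise comparisons with about 450 people.
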